2.3 RISK/BENEFIT ASSESSMENT

2.3.1 KNOWN POTENTIAL RISKS

There is minimal foreseeable additional risk to the patient in the addition of video laryngoscopy to the routine care for their respective procedures. There is a very small risk of damage to teeth or dental work, or trauma to soft tissues of the mouth or oropharynx during insertion of the video laryngoscope following intubation. These risks are similar but smaller in magnitude to the risks of endotracheal intubation, which is already a routine risk of the included procedures.

2.3.2 KNOWN POTENTIAL BENEFITS

There are no direct benefits to the patients enrolled in this study.

We believe that in evaluating how frequently use of the laryngoscopy provides useful information in situations of ambiguous data from the nerve monitor, or in cases of equipment malfunction or failure of the nerve monitor, we would be able to assess whether routine use of the laryngoscopy is needed. This would perhaps prevent situations in which surgeons have insufficient information from nerve monitoring alone.

2.3.3 ASSESSMENT OF POTENTIAL RISKS AND BENEFITS

There is minimal foreseeable additional risk to the patient in this study. The future benefits of potentially prevent situations in which surgeons have insufficient information from nerve monitoring alone outweighs this minimal risk.

3 OBJECTIVES AND ENDPOINTS

OBJECTIVES	ENDPOINTS	JUSTIFICATION FOR ENDPOINTS
Primary 
We seek to assess the degree to which intraoperative video laryngoscopy used in conjunction with routine intraoperative nerve monitoring provides additional data on nerve integrity and vocal cord functions for patients undergoing neck procedures that place the recurrent and superior laryngeal nerves at risk for injury or postoperative dysfunction.
	
As this is a descriptive study, there are no specific patient outcome endpoints. We will be primarily assessing the frequency with which the IOVL provides additional data to IOLNM which may be used to make further surgical decisions.
	
We hope that the addition of IOVL will aid in surgical decision-making and nerve monitoring.

4 STUDY DESIGN

4.1 OVERALL DESIGN

This will be a prospective cohort study without randomization. Patients enrolled will undergo the planned procedure according to our routines of care. IOLNM will be performed per our routine of care.

Additional procedures will involve the following:

- 1) Following consent, but prior to the operation we will complete routine in-office fiberoptic laryngoscopy to assess baseline vocal cord function
- 2) Prior to intubation, the patient will receive glycopyrrolate 0.004 mg/kg, as per typical pre-anesthetic dosing regimen, to decrease airway and mucous membrane secretions
- 3) Upon intubation, the video laryngoscope will be passed under direct vision and secured alongside the endotracheal tube. Vocal cords will be positioned in the visual field of the laryngoscope before beginning the operation
- 4) Following video laryngoscopy, and initiation of the procedure, the ipsilateral vagus nerve will be tested using nerve stimulation (per standard protocol) to ensure good distal nerve conduction and identify potential non-recurrent laryngeal nerve anatomy
- 5) At all points during the procedure where intraoperative nerve monitoring is used, information about vocal cord motion from video laryngoscopy will also be recorded. Specifically, we will record the neuropraxia index from the nerve monitor, and whether vocal cord function is concordant with the neuropraxia index
- 6) At the conclusion of resection, the recurrent and superior laryngeal nerves will be assessed with IONM, the vagus will be assessed with IONM, and lastly the vocal cords will be assessed with IOVL. This sequence is consistent with the describe protocol for IONM for testing the vagus and recurrent nerve prior to resection, and then again in reverse order following resection (V1R1R2V2).
- 7) After conclusion of the procedure and final surgical closing, prior to extubation, vocal cord function will again be assessed with video laryngoscopy
- 8) At standard 1-week and 3-month post-operative follow-up we will also perform routine fiberoptic laryngoscopy, per common practice, to assess vocal cord function. Patients will be asked to complete a brief questionnaire at both of these visits

Medical records will be used to collect the vast majority of data required for this study. In addition, patients will be asked to complete a brief questionnaire at both the standard 1-week and 3-month follow up visits.

Research activities will occur at the Mount Sinai Hospital, Mount Sinai Beth Israel, Mount Sinai Morningside, and Mount Sinai West.

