1 PROTOCOL SUMMARY

1.1 SYNOPSIS

Title:	Intraoperative video laryngoscopy as adjunct for nerve monitoring
Grant Number:	N/A
Study Description:	
The purpose of this study is to describe the impact of adding intraoperative video laryngoscopy (IOVL) to intra-operative laryngeal nerve monitoring (IOLNM) during neck procedures when IOLNM is routinely used, including thyroidectomy and re-operative parathyroidectomy. Specifically, we seek to assess how frequently the use of IOVL provided confirmatory or additional information that may affect surgeon decision-making when IOLNM alone is ambiguous, or when there is equipment malfunction or failure. The IOVL is a disposable, otherwise standard fiberoptic laryngoscope (Larynxview, Neurovision Medical, Ventura CA) that is inserted alongside the endotracheal tube following intubation for surgical procedures. It allows assessment of vocal cord movement in response to nerve stimulation. Currently, the use of IOLNM is based on audio cues, and visual assessment of external laryngeal muscle movement during surgery in response to stimulation, but no direct assessment of vocal cord movement is routinely possible. This information can be ambiguous and subject to judgement of the surgeon. The addition of IOVL provides direct assessment to vocal cord movement in response to stimulus, and may be useful in light of ambiguous IOLNM data, or limited visualization of external laryngeal muscles.

Objectives* :	
This is a descriptive study in which we seek to assess the degree to which intraoperative video laryngoscopy used in conjunction with routine intraoperative nerve monitoring provides additional data on nerve integrity and vocal cord function for patients undergoing neck procedures that place the recurrent and superior laryngeal nerves at risk for injury or postoperative dysfunction. Specifically, we are interested in how frequently the information gained from video laryngoscopy may provide data on the vocal cord function in situations of ambiguous data from the nerve monitor, or in cases of equipment malfunction or failure of the nerve monitor. We would also like to assess the frequency of discordance in evaluation of intraoperative nerve monitoring, which is an indirect measure of vocal cord function via nerve integrity, with direct evaluation of vocal cord function via video laryngoscopy

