IOLNM is an indirect measure of vocal cord function. It provides information on nerve integrity via electromyography (EMG). The feedback the surgeon receives from the system is based on the amount of current necessary to stimulate vocal cord movement, with higher currents indicating worse signal transduction through the nerve, and a loss of signal indicating a severely injured or divided nerve. Surgeons are extrapolating vocal cord function based on auditory cues which indicate nerve integrity, as well as graphical information of the amplitude of the signal (known as the NPI or nerve power index), but do not routinely visualize vocal cord function in real time when making decisions during the procedure. In our experience, the current system has some limitations. The nerve power index (NPI) is a value displayed by the IOLNM system as an expression of nerve function, with higher numbers indicating better nerve conduction. The quality of conduction is audibly expressed by a two-tone system, with a higher-pitched tone occurring with an NPI >100, and a lower-pitched tone occurring with an NPI <100. Often the actual NPI is very close to 100, either higher or lower, and interpretation of nerve integrity in this range is ambiguous. Direct interpretation of vocal cord function could be of greater use to the surgeon at these times. We have also experienced system failures, either due to a break in the small wires of the electrode leads, or computer hardware or software malfunction, any of which can lead to the inability to use the IOLNM. In our experience, some form of failure or malfunction of the IOLNM system occurs in 10-15% of operative cases.

>100, and a lower-pitched tone occurring with an NPI <100. Often the actual NPI is very close to 100, either higher or lower, and interpretation of nerve integrity in this range is ambiguous. Direct interpretation of vocal cord function could be of greater use to the surgeon at these times. We have also experienced system failures, either due to a break in the small wires of the electrode leads, or computer hardware or software malfunction, any of which can lead to the inability to use the IOLNM. In our experience, some form of failure or malfunction of the IOLNM system occurs in 10-15% of operative cases.

Visualization of vocal cord function through an independent system offers another means to assess recurrent laryngeal nerve integrity in these situations.

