4.3 JUSTIFICATION FOR INTERVENTION

Currently, the use of IOLNM is based on audio cues, and visual assessment of external laryngeal muscle movement during surgery in response to stimulation, but not direct assessment of vocal cord movement is routinely possible. This information can be ambiguous and subject to judgement of the surgeon. The addition of IOVL provides direct assessment to vocal cord movement in response to stimulus, and may be useful in light of ambiguous IOLNM data, or limited visualization of external laryngeal muscles.

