5.5 STRATEGIES FOR RECRUITMENT AND RETENTION

We typically see and operate on 20-25 patients per month in our endocrine surgery practice who undergo thyroid or re-operative parathyroid surgery in whom IOLNM is routine. Over a one-year period this would give us access to 200-250 patients who would meet inclusion criteria. Assuming approximately 25-50% of patients consent to participate, this should comfortably allow us to recruit 75-125 patients over the proposed study period. Based on our experience suggesting a 10-15% incidence of IOLNM system malfunction or failure, this should allow us 8-15 patients with IOLNM malfunction with which to directly compare and describe the information available to the surgeon from routine IOLNM and from the IOVL. The degree to which this information differs will allow us to determine if we think IOVL may provide information that could change outcomes and if further, larger studies are warranted.

Patients will be approached to consent in any one of the clinic spaces used by the investigators on this study. All of these locations are listed above. All surgical procedures will be performed in the operating rooms at Mount Sinai Hospital, Mount Sinai Morningside, Mount Sinai West, and Mount Sinai Beth Israel. Follow up visits will be at the previously described clinic locations.

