6.1.2 ADMINISTRATION AND/OR DOSING

At the patient's standard of care surgery, prior to intubation, the patient will receive glycopyrrolate 0.004 mg/kg, as per typical pre-anesthetic dosing regimen. Upon intubation, the video laryngoscope will be passed under direct vision and secured alongside the endotracheal tube. Vocal cords will be positioned in the visual field of the laryngoscope before beginning the operation. Following video laryngoscopy, and initiation of the procedure, the ipsilateral vagus nerve will be tested using nerve stimulation (per standard protocol) to ensure good distal nerve conduction and identify potential non-recurrent laryngeal nerve anatomy. At all points during the procedure where intraoperative nerve monitoring is used, information about vocal cord motion from video laryngoscopy will also be recorded. Specifically, we will record the neuopraxia index from the nerve monitor, and whether vocal cord function is concordant with the neuopraxia index. At the conclusion of resection, the recurrent and superior laryngeal nerves will be assessed with IONM, the vagus will be assessed with IONM, and lastly the vocal cords will be assessed with IOVL. This sequence is consistent with the described protocol for IONM for testing the vagus and recurrent nerve prior to resection, and then again in reverse order following resection (V1R1R2V2). After conclusion of the procedure and final surgical closing, prior to extubation, vocal cord function will again be assessed with video laryngoscopy.

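### The recording rule captures only the nerve-monitor index, so the study cannot show what video laryngoscopy adds to routine monitoring, which by the protocol's own account also uses visible laryngeal muscle movement

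*Protocol*

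**What the plan says.** Section 3 sets the primary measure: "We will be primarily assessing the frequency with which the IOVL provides additional data to IOLNM which may be used to make further surgical decisions". Section 5.5 describes the comparison in the malfunction cases in the same spirit, as a chance to "directly compare and describe the information available to the surgeon from routine IOLNM and from the IOVL". It adds that the degree of difference will inform whether larger studies are warranted.

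The synopsis (1.1) says what IOLNM consists of: "Currently, the use of IOLNM is based on audio cues, and visual assessment of external laryngeal muscle movement during surgery in response to stimulation". Section 4.3 repeats this description and says that IOVL "may be useful in light of ambiguous IOLNM data, or limited visualization of external laryngeal muscles".

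The recording rule is in section 4.1, step 5: "Specifically, we will record the neuropraxia index from the nerve monitor, and whether vocal cord function is concordant with the neuropraxia index". Section 6.1.2 has the same rule, ending "and whether vocal cord function is concordant with the neuopraxia index". Neither section names the external muscle response, or whether the muscles could be seen, as an item to record.

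Section 2.2 describes the feedback from the monitor more narrowly: "Surgeons are extrapolating vocal cord function based on auditory cues which indicate nerve integrity, as well as graphical information of the amplitude of the signal". Muscle movement does not appear there.

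**The concern.** The stated comparator and the recorded comparator differ. The protocol wants to know what IOVL adds to routine IOLNM, and it names two kinds of cue as the basis of that routine. Only the monitor's side of it is written into the data.

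Two things are at stake. First, when the index is near 100 or missing, the surgeon may still have seen a clear muscle response. With no record of it, an IOVL view that supplied the only information cannot be told apart from one that agreed with a cue already in hand. Second, the protocol gives poor muscle visibility as a reason to use IOVL. Without a record of visibility, those stimulations cannot be identified, so that reason cannot be evaluated.

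A statistical analysis plan can define what counts as additional. It cannot recover an intraoperative observation that nobody wrote down.

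**Working it through.** **1. The passages side by side.**

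| Place | Role | Cues covered |
|---|---|---|
| 1.1, 4.3 | What IOLNM use rests on | Audio cues and visible muscle movement |
| 3 | Primary measure | What IOVL adds to IOLNM |
| 5.5 | Comparison in malfunction cases | Information from routine IOLNM |
| 4.1 step 5, 6.1.2 | What is recorded | Index, and cord concordance with it |
| 2.2 | Feedback from the monitor | Audio cues and displayed index |

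**2. Which cue is lost.** Section 2.2 says the tone is high-pitched above an index of 100 and low-pitched below it. While the monitor works, the recorded index therefore gives the tone as well. (I take the neuropraxia index of 4.1 to be the nerve power index of 2.2.) Muscle movement is not a function of the displayed index, so it is the cue that cannot be rebuilt.

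**3. Effect on the count.** Take the stimulations with a usable IOVL view.
- A = those where index and tone are ambiguous or missing.
- M = those where the muscle response is visible and clear.
- Count beyond the index = |A|.
- Count beyond routine IOLNM = |A| − |A∩M|, which cannot exceed |A|.
- Excess of the first over the second = |A∩M|.

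Write v = |A∩M| / |A|. The count beyond routine IOLNM is then |A|(1 − v). The documents give no value for v, so it may lie anywhere from 0 to 1, and the count anywhere from |A| down to 0. M is not recorded, so the study's own data will not narrow this.

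**4. Where the direction can change.** Suppose IOVL is also credited when the routine cues contradict each other, for example a clear index with no visible muscle response. Call those D. The count becomes |A| − |A∩M| + |D|, which can exceed |A|. The tendency to favour IOVL therefore holds for the rule in step 3, not for every possible rule.

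**5. The one related figure.** Section 5.5 expects 8-15 malfunction cases from 75-125 patients at 10-15%.
- Low end: 75 × 0.10 = 7.5, which rounds to the stated 8.
- High end: 125 × 0.15 = 18.75, not 15.

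That mismatch is a separate matter and does not bear on this point. The figure does not help to size the problem either. The protocol does not say in how many failures stimulation remains possible, nor how often a muscle response would then be seen.

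**The case against.** There is a fair case on the other side, and several parts of it stand.

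- **No counting rule is stated.** Nowhere does the protocol say that IOVL counts as additional whenever the index is ambiguous or missing, and section 9.4.2 is marked N/A. This stands, and it rules out saying that the result is overstated. It does not remove the gap in the data that any counting rule would need.
- **Step 5 suits another objective.** The synopsis and section 2.1 also ask how often nerve monitoring and direct cord evaluation disagree. For that question the index is the right comparator. This stands, and the index record should be kept. The point concerns the additional-information measure only.
- **Confirmation counts by design.** The synopsis seeks confirmatory as well as additional information, and it treats cord movement as something external muscle movement does not show directly. An IOVL view that agrees with a visible muscle response is therefore not worthless. This stands, and it is a reason to report the two kinds of finding apart.
- **IOLNM may mean the device output.** Section 2.2 can be read that way, and the specific questions refer to ambiguous data from the nerve monitor. If that is the intended meaning, sections 1.1, 4.3 and 5.5 need rewording, and the use under limited muscle visibility still could not be evaluated.
- **The cue may be captured elsewhere.** Section 4.1 says medical records supply most data, and section 10.1.9.1 mentions worksheets that are not shown. That is possible, but nothing in the protocol says either holds the muscle response at each stimulation.

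**Conclusion.** The point holds as a mismatch between the stated comparator and the recorded data. If the protocol is followed as written, the study can describe what IOVL adds to the index. It cannot show what IOVL adds to routine IOLNM as sections 1.1 and 4.3 describe it, and it cannot assess IOVL where the muscles are poorly seen. This rests on two assumptions: that IOLNM in section 3 has the meaning given in the synopsis, and that no undisclosed form already records the muscle response.

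A reader might infer more: that the frequency of additional information is overstated, or that only some definite part of the 8-15 malfunction cases would truly depend on IOVL. The documents support neither. They state no counting rule and no visibility rate, and some failures may prevent stimulation altogether. What can be said is that a count against the index alone would tend to favour IOVL, by an amount that cannot be computed.

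This is a descriptive pilot with no hypothesis test, so no error rate is affected. The point is still worth acting on, because the comparison feeds the judgement on further studies and the remedy is cheap.

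**What to change.** In section 4.1, step 5, and in section 6.1.2, add one field per stimulation for external laryngeal muscle response: present, absent or not visible. Have it entered with the index and tone, before the IOVL view is recorded.

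State in section 3 that the comparator is index, tone and muscle response together, and report three counts separately:

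- (a) IOVL supplied information when those cues together were ambiguous or unavailable;
- (b) IOVL confirmed a clear routine reading;
- (c) IOVL was discordant with a clear routine reading.

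Say in advance whether routine cues that contradict each other belong under (a), and show their number, since including them raises that count. Keep the index-only concordance for the discordance objective.

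The synopsis gives the stage as enrolling. If operations have already taken place without the field, report those cases apart as index-only.

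The cost is one more item to record at each stimulation and a wording change, with no new procedure or staff. The headline frequency may come out lower.

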2 INTRODUCTION

2.1 STUDY RATIONALE

We seek to assess the degree to which intraoperative video laryngoscopy used in conjunction with routine intraoperative nerve monitoring provides additional data on nerve integrity and vocal cord function for patients undergoing neck procedures that place the recurrence and superior laryngeal nerves at risk for injury or postoperative dysfunction. We want to see how frequently the information gained from video laryngoscopy may provide data on the vocal cord function in situations of ambiguous data from the nerve monitor, or in cases of equipment malfunction or failure of the nerve monitor. We would also like to assess the frequency of discordance in evaluation of intraoperative nerve monitoring, which is an indirect measure of vocal cord function via nerve integrity, with direct evaluation of vocal cord function via video laryngoscopy.

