6.3 MEASURES TO MINIMIZE BIAS: RANDOMIZATION AND BLINDING

N/A

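### The cord reading is specified only as agreement with the nerve-monitor index, with no scale of its own and no shielding from the index, so the discordance frequency is open to review bias

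*Protocol*

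**What the plan says.** The Synopsis objectives and section 2.1 add an aim to the main question of how often IOVL supplies extra information: "We would also like to assess the frequency of discordance in evaluation of intraoperative nerve monitoring", set against direct evaluation of the cords.

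Section 4.1, step 5, describes the data. It opens generally: whenever the monitor is used, "information about vocal cord motion from video laryngoscopy will also be recorded". It then narrows this to two items: the index from the monitor, and "whether vocal cord function is concordant with the neuropraxia index". Section 6.1.2 repeats the item: "whether vocal cord function is concordant with the neuopraxia index".

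Step 6 of section 4.1 sets the order at the end of resection: nerves by monitor, vagus by monitor, then the cords by IOVL. Section 2.2 describes the monitor's audible output: "a higher-pitched tone occurring with an NPI >100, and a lower-pitched tone occurring with an NPI <100". It adds that values close to 100 are hard to interpret and that a direct view of the cords could help most there.

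Section 6.3, "MEASURES TO MINIMIZE BIAS: RANDOMIZATION AND BLINDING", is marked N/A with no reason given. The protocol does not name the person who reads the video.

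**The concern.** Comparing two methods on the same stimulation needs two readings, each on its own scale, with neither made in the light of the other. Here the second reading is specified as a verdict on the first, so whoever makes the entry must know the index. When cord motion is reduced or doubtful, that knowledge can shape the call.

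At stake is whether the reported discordance frequency describes the two methods or partly describes the observer's expectation. The weakness is sharpest near an index of 100. With no rule for what cord motion agrees with a borderline value, the concordance entry has no fixed meaning there. The fault also lies in what is captured in theatre, so an analysis plan written later could not repair it.

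**Working it through.** **Inputs.** From the protocol: the discordance aim (Synopsis; 2.1), the recorded items (4.1 step 5; 6.1.2), the step 6 order, the two-tone signal (2.2), N/A in 6.3, and the planned 125 patients (Synopsis). There is no figure to reproduce: hypotheses and sample size (9.1, 9.2) are N/A and no discordance rate is stated. Every rate below is an assumption.

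**1. Is cord motion recorded on its own?** The general sentence in step 5 could cover a separate motion entry. The next sentence then specifies two items, the index and concordance, and no grade of motion appears in either section. Because the index is recorded, one might try to recover the cord state from index plus concordance. That works only if every observer used the same known rule, such as a cut at 100. None is stated, and near 100 the recovery fails.

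**2. Is the reading shielded?** The concordance item itself requires knowledge of the index. Monitor-first order is explicit in step 6. For the other step 5 readings the order is not stated. Section 6.3 offers no protection.

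**3. Direction.** Let d be true discordance, f the share of true discordances entered as concordant, and g the share of true concordances entered as discordant. Then

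recorded discordance = d(1 − f) + (1 − d)g.

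With d = 10% and f = 20%:
- g = 0: 0.10 × 0.80 = 8%, below the truth.
- Break-even g = df/(1 − d) = 0.02/0.90 = 2.2%: the loss is cancelled.
- g = 5%: 0.08 + 0.90 × 0.05 = 12.5%, above the truth.

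At f = 20%, break-even g is 0.01/0.95 = 1.1% for d = 5% and 0.04/0.80 = 5.0% for d = 20%. Small false-discordance rates are enough to reverse the sign.

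**4. What an agreement count hides.** Take one reading per patient, n = 125, and two assumed tables (both normal; monitor only abnormal; IOVL only abnormal; both abnormal).
- (112, 6, 6, 1): agreement 113/125 = 90.4%; chance agreement (118² + 7²)/125² = 0.894; kappa = (0.904 − 0.894)/(1 − 0.894), which is 0.09 before rounding.
- (100, 6, 6, 13): agreement 113/125 = 90.4%; chance agreement (106² + 19²)/125² = 0.742; kappa = (0.904 − 0.742)/(1 − 0.742) = 0.63.

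The same agreement percentage is compatible with almost no agreement beyond chance or with substantial agreement. Separate grades would tell these apart.

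**5. Scope.** Where the monitor fails there is no index to agree with. The 1-week and 3-month office laryngoscopies are not concordance readings. Neither is touched.

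**The case against.** The strongest case is that this is a descriptive pilot in which discordance is an additional aim. IOVL is meant to be used together with the monitor, so an unmasked reading matches its intended use for the main question of how often it adds information. That stands, and it confines the point to the discordance aim. Section 5.5 does say that the degree of difference will guide whether larger studies follow, but that sentence comes directly after the monitor-malfunction cases, which are unaffected. I do not rest the point on it.

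Three stronger readings are tempting, and the documents do not support them.

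- A reader might infer that discordance will be understated. Pull toward agreement is the usual expectation, but section 3 states the investigators' hope that IOVL will help, which could push readings the other way. Step 3 of the working shows how little that would take.
- A reader might infer that every observer has already heard the result. The tone is audible, but the video reader is not named, and only step 6 fixes the order. Section 2.2 also ties the tone to a nerve power index while step 5 records a neuropraxia index. That these are the same quantity is likely but not stated.
- A reader might infer that cord motion is certainly not recorded. The worksheets are not shown, and the general sentence in step 5 leaves room for an entry. What holds is that the protocol specifies none.

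It is also fair to say that live grading cannot be fully masked with an audible tone. That limits the remedy but does not justify the present item.

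**Conclusion.** The point holds in limited form. The protocol specifies the cord reading only relative to the index, with no scale, no concordance rule and no shielding, so the discordance frequency is open to review bias. Bias toward agreement is the most plausible direction but is unproven. Its size cannot be estimated from the documents; the rates in the working are assumptions that show only that the sign is not fixed.

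The conclusion assumes that the case report form follows the items named in step 5, and that the neuropraxia index is the quantity behind the two tones. If the form already carries an independent motion grade, what remains is to say so in the protocol and to add the rule and the order of entry. The main question, monitor-failure cases and office laryngoscopies are not called into question. This is worth correcting because the remedy is cheap and the missing information cannot be reliably recovered afterwards.

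**What to change.** 1. In sections 4.1 (step 5) and 6.1.2 alike, replace the concordance item with a predefined cord-motion grade for each stimulation, for example full / reduced / none / not seen. The team member already viewing the scope enters it before the index number is read out.
2. Record the index separately, under one name throughout the protocol.
3. Derive concordance afterwards by a prespecified index rule that includes a category for values near 100, with its limits set by the investigators in advance.
4. Replace N/A in section 6.3 with this procedure.
5. Optional: if the device already saves video, which the protocol does not mention, an investigator already on the team may regrade clips without sound or index as a check.

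The operation and the step 6 testing sequence need not change. The closing IOVL view in step 6 remains a reading made after the monitor and should be labelled as such.

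Cost: new wording, a slightly longer form and a fixed order of entry. It assumes that someone on the team is already watching the scope view. Live grading stays only partly masked because the tone is audible, and regrading clips, if done, takes some investigator time.
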